## 12 PLANNED STATISTICAL METHODS

### 12.1 General Considerations

Data analysis will be performed using SAS® Version 9.2 or higher.

#### Confidentiality Statement

Data and information contained in this document are considered to constitute trade secrets and confidential commercial information, and the legal protections provided to such trade secrets and confidential information are hereby claimed under the provisions of applicable law. No part of this document may be publicly disclosed without the written consent of Philip Morris Products S.A.

Nicotine PK parameters will be derived from plasma nicotine concentrations versus time data by non-compartmental analysis (NCA) and any required data transformation for the PK analysis on the provided analysis PK set will be conducted using Phoenix® WinNonlin® version 7.0 or higher (Certara L.P. (Pharsight), St. Louis, MO).

Data listings will be provided for all data collected as required by the protocol, and including all data derived for analysis purposes, ordered by subject, product variant (if applicable), use regimen (if applicable) and time point (if applicable), unless otherwise stated. Data listings will include all subject level data collected unless otherwise specified.

Summary statistics and statistical analysis will only be presented for data where detailed in this SAP.

Safety data will be summarized for the Safety Population. All endpoints other than safety will be analyzed using the PK population.

### **12.1.1 Stratified Presentation**

Stratified by sex presentations will be conducted on the PK population for the following endpoints:

- Demographics
- Nicotine concentrations in blood
- PK parameters

### **12.1.2 Subgroup Analyses**

No subgroup analyses will be performed in this study.

### **12.1.3 Descriptive Statistics**

For continuous data, summary statistics will include the number (n) of subjects, the number and percent of subjects with missing data, the arithmetic mean and standard deviation (mean and SD), median, first and third quartiles, minimum and maximum.

For log-normal data (e.g., the PK parameters: AUC and Cmax) the geometric mean and geometric CV will be used for interpretation and presented in addition to the arithmetic mean and SD.

For nicotine plasma concentrations, the number and percent of BLOQ samples, the geometric mean, the geometric CV and the 95% confidence interval of geometric mean will be presented in addition.

For categorical data, frequency counts and percentages will be presented.

For the calculation of summary statistics and statistical analysis, unrounded data will be used. However rounding will be performed for the presentation of final results as follows:

- For discrete or continuous data, data will be presented rounded to 3 significant digits when below 1000; and they will be reported with all significant digits apart from the decimal digits when above or equal 1000. Summary statistics below

#### **Confidentiality Statement**

0.0001 will be displayed as 0. The geometric coefficient of variation (CV) will be reported as % with two decimal digits.

- For categorical data, frequency counts and percentages will be presented, missing values will be regarded as an own category if any missing value exists. Percentages will be presented to one decimal place. Percentages will not be presented for zero counts.

All analyses and summaries will be performed by product and overall, and separately for fixed and *ad libitum* use regimen when applicable.

Unless otherwise specified, summaries will be presented at Baseline and at each post baseline timepoint, including the change from baseline (calculated as difference from baseline).

#### **12.1.4 Definitions for Statistical Data Analysis**

Definitions for statistical analyses/presentations are detailed in Section 4.1 "Definitions for Statistical Analysis".

#### **12.1.5 Handling of Dropouts or Missing Data (including outside the limits of quantitation)**

For the derivation of PK parameters:

- Any missing value for baseline concentration (for both fixed regimen and *ad libitum* use) will be considered as 0 while no imputation will be performed for missing concentration values for all other endpoints.
- Values below the lower limit of quantitation (BLOQ) will be set to missing and ignored apart from:
  - BLOQ values before  $T_0 \text{ fix}$  or  $T_0 \text{ ad lib}$  are considered as zero. The same rule will be applied for each individual plasma concentration value between  $T_0 \text{ fix}$  (respectively  $T_0 \text{ ad lib}$ ) and the first time point above LLOQ.
  - BLOQ values after the last quantifiable value are not included in the analysis.
  - Any other BLOQ value (after  $T_0 \text{ fix}$  or  $T_0 \text{ ad lib}$  and before the last quantifiable value) would need to be queried and, if confirmed, it will be imputed by LLOQ/2. Otherwise the value will not be included in the analysis.

For the summary and the figures of nicotine concentration and laboratory parameters values:

- No imputation will be performed for missing concentration, summaries will be performed on available data.
- BLOQ values after  $T_0 \text{ fix}$  or  $T_0 \text{ ad lib}$  and before the last quantifiable value would need to be queried and, if not confirmed, it will be excluded from summary and figures. Other BLOQ values will be imputed by LLOQ/2.
- For values above the upper limit of quantitation (ULOQ), i.e. preceded by a ">", for example ">xx," the numerical xx will be used.

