### 7.1.2.1 Calculation of $C_{\text{max}}$ , $t_{\text{max}}$ , $C_{\text{peak}}$ , $t_{\text{peak}}$ with and without baseline adjustment

The minimum requirement for the determination of the  $C_{\text{max}}$  is the inclusion of at least one quantifiable concentration within 1 hour post-exposure.  $C_{\text{max}}$ ,  $t_{\text{max}}$ ,  $C_{\text{peak}}$ ,  $t_{\text{peak}}$  will be obtained directly from the plasma concentration-time profiles. If  $C_{\text{max}}$  (respectively  $C_{\text{peak}}$ ) occurs at more than one time point,  $t_{\text{max}}$  (respectively  $t_{\text{peak}}$ ) will be assigned to the first occurrence of the  $C_{\text{max}}$  (respectively  $C_{\text{peak}}$ ).

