**Table 15 Definition of Minor Protocol Deviation Categories**

Category	Description
Procedural violation	Violation of any study procedures not affecting safety or data evaluability
Time deviation (Plasma nicotine PK sample)	Assessments not taken at the correct time or within the allowed time window or date/time is missing (see Table 16)
Time deviation (other assessment)	Assessments not taken at the correct time or within the allowed time window or date/time is missing (see Table 16)
Assessment missing (Plasma nicotine PK sample)	Assessment is missing
Assessment missing (other assessment)	Assessment is missing
Randomization sequence	Subject randomized not according to the sequence of the subject numbers assigned during the screening visit

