### **Confidentiality Statement**

15.2.3.2.1 for uncorrected concentrations, Tables 15.2.3.3 and 15.2.3.3.1 for background-corrected PK parameters, Tables 15.2.3.4 and 15.2.3.4.1 for uncorrected PK parameters).

The individual uncorrected and background-corrected plasma nicotine concentrations and actual sampling times will be listed (Listing 15.3.3.1).

The individual uncorrected and background-corrected PK parameters will be listed (Listing 15.3.3.2).

The individual plasma nicotine concentrations up to 4 hours will be plotted by P3P variant in a linear and semi-logarithmic scale (Figures 15.1.3.1 and 15.1.3.2 for background-corrected concentrations, Figures 15.1.3.3 and 15.1.3.4 for uncorrected concentrations).

The geometric mean plasma nicotine concentrations up to 4 hours will be plotted by P3P variant and their 95% CI (Figures 15.1.3.5 and 15.1.3.6 for background-corrected concentrations, Figures 15.1.3.7 and 15.1.3.8 for uncorrected concentrations).

Boxplots of  $cC_{max}$ ,  $cAUC_{fix(0-4h)}$ ,  $C_{max}$  and  $AUC_{fix(0-4h)}$  by P3P variant will be presented (Figure 15.1.3.9- 15.1.3.12).

A mixed model will be conducted on logarithmically transformed PK parameters for  $cC_{max}$ ,  $cAUC_{fix(0-4h)}$ ,  $C_{max}$  and  $AUC_{fix(0-4h)}$  with fixed terms for sequence, product variant and two dummy variables for Day 3 and Day 4 (i.e two variables taking value 1 for Day 3 and Day 4 respectively and value 0 for the other study days) and using subject nested within sequence as random effect. In this way Day 1 and Day 2 will be combined to address the multicollinearity as planned in the protocol. The SAS code to be used is shown below:

```
proc mixed data=_data_;  
  class Sequence Product_Variant Day3 Day4 Subject;  
  model logPK_Parameter = Sequence Product_Variant Day3 Day4 / ddfm=SAT s;  
  random Subject(Sequence) / sub=Subject type=CSH;  
  lsmeans Product_Variant / cl diff alpha=0.05;  
run;
```

In case of model convergence issues, this will be reported in the study report and the variance component (type=VC) covariance structure will be investigated.

Geometric least square means and ratios will be presented for the analysis of  $cC_{max}$ ,  $cAUC_{fix(0-4h)}$ ,  $C_{max}$  and  $AUC_{fix(0-4h)}$  together with 95% CI by sex and overall for the following effects of interest (Tables 15.2.3.5, 15.2.3.5.1, 15.2.3.6 and 15.2.3.6.1):

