#### **13.1.3.1 Primary PK Analysis Methodology (NCA-based method)**

The nicotine terminal elimination rate constant  $\lambda_z$  (and  $t_{1/2z}$ ) will be estimated as described in Section 7.1.2.3 "Criteria for Calculating the Apparent Terminal Elimination Half-Life". For the purposes of background-correction of the plasma concentrations post-baseline the following formula will be applied:  $cC_t = C_t - C_0 \cdot e^{-\lambda_z \cdot t}$ . Where  $cC_t$  is the corrected concentration at each time point,  $C_t$  is the concentration at each time point,  $C_0$  is the pre-use baseline concentration,  $\lambda_z$  is the terminal elimination rate constant and  $t$  is the actual time.

If the predicted  $cC_t$  is  $< 0.2$  ng/mL (the bioanalytical LOQ threshold), this value will be used for the estimation of the background-corrected PK parameter (NCA analysis) only if the corresponding  $C_t$  is above LOQ, and the predicted  $cC_t$  will be imputed by zero if

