#### **Confidentiality Statement**

negative. The derivation of  $cC_t$  from  $C_t$  values BLOQ will follow rules specified in section 12.1.5.

To evaluate the applicability of this background-correction method, the number of subjects for whom  $\lambda_z$  can be robustly estimated from the PK samples collected at Days 4 to 5 (see section 7.1.2.3 "Criteria for Calculating the Apparent Terminal Elimination Half-Life") will be considered, as this will limit the number of evaluable subjects for the background-corrected PK analysis.

If  $\lambda_z$  cannot be reliably estimated (see Section 7.1.2.3 "Criteria for Calculating the Apparent Terminal Elimination Half-Life") for a relevant number of subjects (e.g. for at least 80% of the PK population) then an alternative approach described in the next section will be evaluated.

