### **13.1.3.2 Alternative PK Analysis Methodology (CA-based method)**

Based on a visual examination of the concentration/time profiles, different potential compartmental PK models will be assessed. As a starting point, a two-compartment linear disposition combined with zero-order absorption model will be considered as this has previously been found to adequately describe the absorption phase and the biphasic disposition of plasma nicotine following administration via other smoking devices (*Marchand et al., 2017*).

For the purpose of this analysis the following assumptions in terms of nicotine exposure ("dose") will be made:

1. The nicotine content in the P3P capsule (1 or 2 mg) multiplied by the before and after use 'weight differential' ( $\Delta W = W_{\text{before}} - W_{\text{after}}$ ) is directly proportional to the nicotine intake ( $[\text{P3P capsule nicotine content} \times \Delta W] \propto \text{nicotine exposure}$ ) and will be used as a surrogate 'dose' for the inhaled nicotine exposure (intake) for the purposes of modelling, for both fixed and ad libitum regimens.
2. For fixed regimens, duration of puffing and the Human Puffing Topography (HPT) parameters are the same in all study subjects.
3. The smoking start and stop time will be used as the nicotine intake duration. For any other occasions where the nicotine exposures or duration of smoking are unknown (e.g. Day -1) these will be estimated during the model fitting.

After successfully fitting the individual plasma nicotine data with a PK model, the same approach described in Section 13.1.3.1 will be adopted to derive corrected nicotine levels by means of subject-specific  $\lambda_z$  predicted by the model. General equations for determination of  $\lambda_z$  from the parameters estimated in a two-compartment model are presented below:

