### **13.1.3.3 Population PK Analysis Methodology (Non-Linear Mixed Effects Modelling)**

In the event that the two previously described PK analysis methods fail in background-correcting the data, a population PK analysis approach will be used.

This method will involve pooling the data from the present study with that of previous Philip Morris clinical studies and fitting this new dataset with the previously described population PK model by Marchand et al. (*Marchand et al., 2017*) to ultimately obtain the post hoc individual estimates of the PK parameters and the corresponding background-corrected individual PK parameters ( $C_{max}$ ,  $AUC_{(0-4h)}$ ) for subjects in study P3P-PK-01-CH.

Once individual parameters are obtained, PK simulations will be generated for each individual and P3P variant so as to obtain the corresponding background-corrected exposure PK parameters (e.g.  $cC_{max}$ ,  $cAUC_{fix(0-4h)}$ , etc.).

Similar to the compartmental analysis method, an important caveat for its applicability is that it requires knowledge of the actual nicotine exposure after both fixed puffing as well as ad libitum regimens (i.e. a reasonably accurate data on the nicotine input into systemic circulation over time).

The data will be explored graphically to evaluate its a priori fitness for modeling via this method (e.g. missing data, completion of the PK profiles, outliers etc.). If a population PK analysis methodology is to be considered a stand alone Modeling Analysis Plan (MAP) will be written. Although the final decision on the method for nicotine adjustment should be taken before the database lock, the MAP may be finalized after db lock.

In case the population PK method is also deemed unsuccessful, only the uncorrected PK parameters will be reported and used for statistical analyses.

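### Setting a missing pre-use nicotine concentration to 0 lets that session's uncorrected values into the background-corrected analyses (wrong as written, low impact)

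*SAP*

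**What the plan says.** SAP 12.1.5, under the rules for deriving PK parameters, states that "Any missing value for baseline concentration (for both fixed regimen and *ad libitum* use) will be considered as 0". The same bullet rules out imputing any other missing concentration.

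SAP 13.1.3.1 introduces the correction with the words "background-correction of the plasma concentrations post-baseline the following formula will be applied": cC_t = C_t − C_0·exp(−λz·t), where C_0 is the pre-use baseline. The compartmental alternative in SAP 13.1.3.2 changes only the source of λz; after the model fit, "the same approach described in Section 13.1.3.1 will be adopted to derive corrected nicotine levels".

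Protocol 4.2 gives half-lives of 1.35 h (initial) and 17 h (terminal), says full washout would need 3 days, and sets a minimum of 10 h between starts of use. SAP 7.1.2 gives carry-over from this limited washout as the reason for the correction.

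No rule takes an affected session out of the corrected analysis. SAP Table 15 classes a missing plasma nicotine sample as a minor deviation, whereas SAP 11 reviews major deviations for exclusion from the PK population. The Cmax rule in SAP 7.1.2.1 asks only for "the inclusion of at least one quantifiable concentration within 1 hour post-exposure". The AUC rule in SAP 7.1.2.2 asks for three quantifiable values, one of them after the peak. Neither asks for a baseline.

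**The concern.** In ordinary non-compartmental work, a zero at time zero affects only the first trapezoid. Here C0 is also the quantity subtracted from every later concentration, so a zero switches the correction off for that session. The result still carries the corrected label and enters cCmax and cAUC (primary, fixed puffing) or cCpeak, cCtrough, cCaverage and cAUC (secondary, *ad libitum*) as a valid record.

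The error has one direction. It raises the affected variant's geometric mean. A ratio of P3P 2 to another variant rises if the affected record is P3P 2 and falls if it is the comparator.

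Zero is also not a neutral value in this design: exp(−ln2 × 10/17) = 0.665, so two thirds of a terminal-phase concentration remains after 10 h. Day 1 is exposed too, because the subjects are smokers with only 10 h of required abstinence.

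**Working it through.** The plan gives no figure for this, so there is none to reproduce. The check puts C0 = 0 into the plan's own formula.

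**Inputs from the documents**
- Half-lives of 17 h and 1.35 h (Protocol 4.2); λz = ln2/17 = 0.0408 per h.
- Sampling times (SAP Table 16), with the pre-use sample placed at time zero (SAP 7.1.2); linear trapezoids (SAP 7.1.2.2).
- LOQ of 0.2 ng/mL (SAP 13.1.3.1).
- 18 randomised subjects, at least 8 of each sex (SAP 6.3.1).
- Cmax of 9.7 ng/mL for P3L, a different product (Protocol 2.1.2), used for scale only.

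**Assumptions:** a low peak of 3 ng/mL, which has no source in the documents; a rise to the peak at 7 min; then biexponential decline with 10 to 20% of the peak in the slow phase.

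**Background left in, per unit of true C0.** The correctly adjusted curve is zero at time zero, so the retained background is exp(−λz·t) with a zero first node.
- Fixed, at a 7 min peak: exp(−0.0408 × 7/60) = 0.995.
- Fixed, cAUC(0-4h): trapezoid sum 3.68 h.
- *Ad libitum*, cCpeak: 0.993 for a peak at 10 min, 0.960 at 1 h.
- *Ad libitum*, cCaverage over 0-1 h: 0.897. cAUC(0-4h): 3.61 h.

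**A plausible C0.** At 9.75 h after one earlier session (10 h less the 15 min lead), the assumed profile leaves 0.72 ng/mL (10% slow share) to 1.37 (20%) at peak 9.7, and 0.22 to 0.42 at peak 3. The illustration therefore runs to 1.4 and 0.5 ng/mL. Its lower end is the LOQ, because a measured value below it counts as zero anyway. Several earlier sessions, heavier *ad libitum* use or smoking before admission would leave more, and the bias grows in proportion.

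**Inflation of one fixed session.** The assumed true AUC(0-4h) is 19.2 to 21.0 ng·h/mL at peak 9.7 and 5.94 to 6.50 at peak 3.

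| Peak | C0 | cCmax | cAUC(0-4h) |
|---|---|---|---|
| 9.7 | 0.2 | 0.2 × 0.995/9.7 = 2.1% | 0.2 × 3.68/21.0 = 3.5% |
| 9.7 | 1.4 | 1.4 × 0.995/9.7 = 14.4% | 1.4 × 3.68/19.2 = 26.8% |
| 3 | 0.2 | 0.2 × 0.995/3 = 6.6% | 0.2 × 3.68/6.50 = 11.3% |
| 3 | 0.5 | 0.5 × 0.995/3 = 16.6% | 0.5 × 3.68/5.94 = 31.0% |

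Pairing the largest C0 with the smallest AUC makes the upper ends deliberately wide.

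**Effect on the summaries.** One affected record among n multiplies a geometric mean by (inflation)^(1/n).
- n = 18, cCmax: 1.021^(1/18) = 1.001 to 1.166^(1/18) = 1.009.
- n = 18, cAUC: 1.035^(1/18) = 1.002 to 1.310^(1/18) = 1.015.
- Smallest sex stratum, n = 8: at most 1.310^(1/8) = 1.034.

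In the mixed model of SAP 12.6.1 with complete data, a P3P 2 record has weight 3/54 in the contrasts with P3P 1 and P3P 4. In P3P 2 vs P3P 3 its weight is 5/54 on Day 2 and 2/54 on Day 3 or 4. The largest weight moves that ratio by at most 1.166^(5/54) = 1.014 for cCmax and 1.310^(5/54) = 1.025 for cAUC.

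**Keep or drop a single affected record.** Keeping it adds squared bias; dropping it adds variance. I refitted the SAP model for 18 subjects with one P3P 2 record affected, assuming a between-subject CV of 40%. Dropping gives the lower mean squared error only if the inflation exceeds about 13% at a within-subject CV of 10%, 20% at 15%, 27% at 20% and 42% at 30%. The documents give no CV.

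**The case against.** The strongest reply is that this will rarely, if ever, matter. Subjects are confined and supervised at one site, the pre-use sample is scheduled in every session, and nothing in the documents shows that any is missing. The study tests no hypothesis (SAP 5.4.1), and SAP 12.1.8 says no claim will rest on individual intervals. An affected session would also be visible: in SAP 12.6.1 "The individual uncorrected and background-corrected PK parameters will be listed", the interim report lists imputed data, and a data review meeting precedes lock. All of this stands and keeps the point minor. But visibility does not correct the value, and no rule tells the analyst to act on it.

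A second reply is that deletion may not improve the estimate. That also stands for a single record, as the break-even figures show. The case for deletion is that it removes a known upward bias and a wrong label, not that it always reduces error. Bias would accumulate over several affected records in one variant.

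Three stronger readings are tempting and are not supported:
- *The SAP contradicts the protocol.* Protocol 12.1.4 says only that missing data are, in general, not imputed, and Protocol 12.5.1 leaves the baseline adjustment to the SAP. A specific SAP rule is permitted; the fault is its content.
- *Zero for a pre-use value below quantification is equally wrong.* A measured value below 0.2 ng/mL bounds C0; a missing sample bounds nothing.
- *Every route to the primary results is affected.* The population PK route obtains corrected parameters from simulation and need not use the zero. If that route also fails, SAP 13.1.3.3 says "only the uncorrected PK parameters will be reported and used for statistical analyses", and there is then no subtraction to lose.

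**Conclusion.** The rule is wrong as written and its impact is low. Under the non-compartmental and compartmental corrections, a session without a pre-use sample is analysed as corrected although nothing was subtracted, in a design that expects residual nicotine. The factors on C0 follow from the SAP formula and the 17 h half-life.

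The percentages are illustrative only, since C0, the true peak and the number of missing baselines are unknown: about +2 to +17% on cCmax and +4 to +31% on cAUC for an affected fixed session, and about 0.1 to 1.5% on an 18-record geometric mean.

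A reader might infer that the reported corrected results are biased. The documents do not show that, because the effect is nil unless a baseline is missing.

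**What to change.** In the first bullet of SAP 12.1.5, replace the zero rule with:

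> If the pre-use sample of a session is missing, all background-corrected concentrations and parameters of that session are set to missing in the summaries, figures and models and flagged in the listings. Uncorrected concentrations and parameters are kept; for uncorrected AUC and Caverage only, the time-zero value is taken as 0 and the result is flagged.

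Corrected concentrations must be included: the concentration-time profile is itself a primary endpoint, and SAP 12.6.1 tabulates, lists and plots it. Keeping the zero for uncorrected AUC and Caverage does little harm. It lowers the fixed AUC by 0.5 × 2/60 = 0.017 h × C0, the *ad libitum* AUC by 0.5 × 10/60 = 0.083 h × C0, and Caverage by 0.083 × C0. Leave the rules for values below quantification unchanged.

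The cost is one bullet, a small programming change and an occasional lost corrected record. SAP 13.1.3.1 already accepts a comparable loss at subject level where λz cannot be estimated ("this will limit the number of evaluable subjects for the background-corrected PK analysis"), although it does not provide for dropping single sessions. Because the lost precision can exceed the bias removed for one record, the present zero rule can be kept as a sensitivity analysis. Under the compartmental route, a pre-use level predicted by the subject's fitted model could serve the same purpose.
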